6.8 Pharmacodynamic Analysis

Observed values and change from baseline of PPG concentrations will be summarized by treatment group and time point in terms of the number of subjects, arithmetic mean, SD, CV%, median, minimum and maximum. Baseline for PPG concentrations will be the pre-dose (Hour 0) value of the PPG profile on each PPG collection day. Concentrations will be listed, mean and individual plots will also be presented.

The plasma glucose excursion defined as the maximum glucose value observed after breakfast (0-4 hours after breakfast) minus the pre-dose (Hour 0) value will also be summarized for observed values and change from baseline on Days -1, 1, 14 and 28. Day -1 will be baseline.

Area under the observed effect-time curve from the time of starting breakfast until the 4-hour time point (AUEC₀₋₄) will be calculated for PPG on Days -1, 1, 14 and 28 for the PD population. Observed values and change from baseline of AUEC₀₋₄ will be summarized descriptively. Baseline will be the corresponding parameter value on Day -1.

A linear mixed effect model including day as the fixed effect and subject as the random effect will be fitted on the the PD parameter for each treatment group separately. The difference of the least square means of AUEC₀₋₄ between the compared days (Day 1 vs. Day -1, Day 14 vs. Day -1, Day 28 vs. Day -1 and Day 28 vs. Day 14) and the 90% and 95% CIs of the least square mean difference will be calculated.

The following sample SAS code may be used, with appropriate changes, for the analysis:

```
PROC MIXED DATA=DATASET;
BY TREATMENT:
  CLASS SUBJID DAY;
  MODEL PDPARVAL = DAY / DDFM=KR;
  RANDOM SUBJID;
  LSMEANS DAY / CL;
  ESTIMATE 'Day 1 Vs. Day -1' Day 1 0 0 -1/ALPHA = 0.05 CL;
  ESTIMATE 'Day 14 Vs. Day -1' Day 0 1 0 -1/ALPHA = 0.05 CL;
  ESTIMATE 'Day 28 Vs. Day -1 ' Day 0 0 1 -1/ALPHA = 0.05 CL;
  ESTIMATE 'Day 28 Vs. Day 14 'Day 0 -1 1 0/ALPHA = 0.05 CL;
  ESTIMATE 'Day 1 Vs. Day -1' Day 1 0 0 -1/ALPHA = 0.1 CL;
  ESTIMATE 'Day 14 Vs. Day -1' Day 0 1 0 -1/ALPHA = 0.1 CL;
  ESTIMATE 'Day 28 Vs. Day -1 ' Day 0 0 1 -1/ALPHA = 0.1 CL;
  ESTIMATE 'Day 28 Vs. Day 14 ' Day 0 -1 1 0/ALPHA = 0.1 CL;
 RUN;
```

[figure not shown]
Statistical Analysis Plan - Protocol No. AT662-U-20-003

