Additionally, the change from baseline (Day -1) of AUEC₀₋₄ will be analyzed using the mixed effect model with repeated measures (MMRM). The model will include fixed effects for treatment, day, and treatment by day interaction, subject as repeated measures and baseline value as a covariate. The difference of the least squares means between each JTT-662 dose group relative to placebo at the same day will be estimated, along with two-sided 90% and 95% CIs and p-values. Least squares means will also be presented.

[figure not shown]
The following sample SAS code may be used, with appropriate changes, for the analysis:

```
PROC MIXED DATA=DATASET;
 CLASS DAY TREATMENT;
 MODEL CHG = DAY TREATMENT DAY*TREATMENT BASELINE / DDFM=KR;
 REPEATED /SUBJECT=SUBJECT(TREATMENT) TYPE=UN*;
 LSMEANS DAY*TREATMENT /PDIFF CL ALPHA=0.1**;
RUN:
```

^{**} alpha = 0.05 and 0.1.

^{*} Other covariance structure will be used if UN leads to non-convergence of the model.

Statistical Analysis Plan - Protocol No. AT662-U-20-003

6.10 **Analysis of Safety Data**

Safety analyses will be conducted on the Safety Population and will be performed for all safety variables specified below.

The safety evaluation will include AEs, clinical safety laboratory tests (e.g., hematology, serum biochemistry, coagulation, urinalysis), vital signs, 12-lead ECGs, BSC findings, ketone bodies, urinary calcium excretion from the time of dosing until the 24-hour time point (UCE₀₋₂₄) and urinary sodium excretion from the time of dosing until the 24-hour time point (UNa E_{0-24}) and UGE $_{0-24}$.

Observed and change from baseline of vital signs, ECG parameters and clinical laboratory data will be presented in tabular form with arithmetic mean, SD, median, minimum and maximum, or in frequency tabulation form as appropriate. For the laboratory safety data, out of range values and PCS abnormalities will be flagged in the data listings.

Potentially clinically significant abnormalities will be defined according to the Akros Safety Reporting Standards Potentially clinically significant values for vital signs, ECG, and laboratory data will be flagged in data listings.

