6.10.6 Other Safety Data

Observed values and change from baseline of ketone bodies will be summarized by treatment group and time point.

Listing with subjects impacted by COVID-19 will be presented. Also, eGFR values will be listed.

Urine Calcium, Glucose and Sodium

The UCE₀₋₂₄, UGE₀₋₂₄ and UNaE₀₋₂₄ will be computed for Days -1, 1, 14 and 28. Observed values and change from baseline (Day -1) of total excreted amount within 24 hours will be summarized by treatment group and day. Descriptive statistics for 24-hour urine volume and fluid intake on Days -1, 1, 14 and 28 will be also presented for observed values and change from baseline.

Statistical analysis for change from baseline in UGE_{0-24} in the original scale will be performed using MMRM similar to that for PPG AUEC₀₋₂₄.

Bristol Stool Chart

Total number of stools and percent of stools at each stool type will be summarized by treatment group. Post-treatment highest stool type score will be also derived for each subject, and number and percent of subjects by the highest stool type will be summarized by treatment group and overall. A plot will be created for individual assessments over time.

Other safety parameters may be summarized as appropriate.

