6.12 Handling of Dropouts or Missing Data

Missing data will not be imputed. Any PK concentrations reported missing data will be handled according to the specifications in Section 4.2.

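### The MMRM sample code in SAP 6.8 leaves subject out of CLASS and day out of REPEATED, so as printed it either errors or depends on row order: a minor, cost-free correction

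*SAP*

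**What the plan says.** SAP 6.8 Pharmacodynamic Analysis describes an MMRM for change from Day -1 in AUEC0-4. Treatment, day and their interaction are fixed effects, with "subject as repeated measures and baseline value as a covariate". Each dose is compared with placebo on the same day, with 90% and 95% intervals and p-values.

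The code is introduced by "The following sample SAS code may be used, with appropriate changes, for the analysis". Two of its lines matter here:

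- the class statement, "CLASS DAY TREATMENT";
- the repeated statement, "REPEATED /SUBJECT=SUBJECT(TREATMENT) TYPE=UN".

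A footnote adds: "Other covariance structure will be used if UN leads to non-convergence of the model". The within-group model printed just before it, in the same section, has "CLASS SUBJID DAY". It therefore classes both subject and day, under a different subject variable name.

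Three other places bear on the point. SAP 6.12 says "Missing data will not be imputed". The opening of the SAP's Statistical Methods section fixes a sort order, but for data listings only. SAP 6.10.6 plans the UGE0-24 analysis "using MMRM similar to that for PPG", and the parameter it then names is AUEC0-24, whereas the MMRM shown in 6.8 is for AUEC0-4.

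**The concern.** An unstructured covariance over Days 1, 14 and 28 means something only if each record is tied to its subject and its day. The printed code does neither explicitly.

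In PROC MIXED (general software knowledge, not taken from the documents), a numeric subject variable outside CLASS starts a new block whenever its value changes from one row to the next. With no repeated effect, the k-th row of a block takes covariance position k. The fitted model then depends on how the dataset happens to be sorted and on which rows it contains. The SAP specifies neither for the model dataset. The footnote does not help, because it is triggered only by non-convergence.

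At stake are the standard errors, intervals and p-values for each dose against placebo on AUEC0-4, and those for UGE0-24 if the same template is carried over.

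**Working it through.** The plan states no SD, power or expected missingness, so there is no figure of its own to reproduce. The check has two parts: what the code does in each data situation, and how large the effect is under assumed SDs.

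**Inputs from the documents**

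- Three cohorts of 9 active and 3 placebo (SAP 3), with placebo pooled (SAP, Statistical Methods): 4 groups of 9, so 36 subjects.
- Post-baseline Days 1, 14 and 28: 36 × 3 = 108 records if complete.
- Fixed effects: 4 × 3 = 12 treatment-by-day means plus 1 baseline slope = 13 parameters.

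**Assumed inputs**

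- SDs by day of 1:1:1, 90/95/100, 60/90/100 or 1:1.5:2.
- Within-subject correlation of 0.5 to 0.7.
- 2 to 6 absent records in most cases (15% of Day 14 records in one).
- In the checks with degrees of freedom shown here, t intervals with 36 − 5 = 31 df for the correct model, and 108 − 13 = 95 df when every row is its own block, in place of Kenward-Roger.

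**Step 1. No effect.** For complete data sorted by subject then day, the half-width ratio (printed code over correct code) is 1.00/1.00/1.00 on Days 1/14/28. With Day 28 absent in 4 subjects it is again 1.00/1.00/1.00, since no position shifts. Empty rows kept for missing days also hold the positions.

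**Step 2. An earlier record absent and a later one present.** The later day moves up one position. With 6 of 36 (16.7%) absent:

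| Absent day | SDs | Mean half-width ratio, Days 1/14/28 | Mean absolute change per trial |
|---|---|---|---|
| Day 14 | 1:1:1 | 1.00/1.00/0.99 | 0.4%/3.8%/3.2% |
| Day 14 | 1:1.5:2 | 1.00/1.05/0.96 | 0.5%/6.9%/4.6% |
| Day 1 | 1:1:1 | 1.01/0.99/1.00 | 3.4%/4.5%/3.0% |
| Day 1 | 1:1.5:2 | 1.06/0.97/0.97 | 7.8%/6.5%/4.2% |

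With 15% of Day 14 records absent and SDs 60/90/100, the mean Day 28 standard error is 46.0–46.1 by row order against 47.0–47.4 aligned by day, a shift of about 2–3%. With 2 absent records the mean absolute change is about 0–4%.

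**Step 3. Dataset sorted so that every row is its own block** (for example by treatment, day, subject). The unstructured matrix collapses to one common variance, whose expectation is about the mean of the three day variances. So:

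- SE ratio on day d ≈ √[(σ₁² + σ₁₄² + σ₂₈²)/3] / σ_d.
- Half-width ratio = SE ratio × t(0.975; 95)/t(0.975; 31) = SE ratio × 1.985/2.040 = SE ratio × 0.973.
- Approximate coverage = 2Φ(1.985 × SE ratio) − 1.

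For 1:1.5:2, √[(1 + 2.25 + 4)/3] = √2.417 = 1.555. The Day 28 SE ratio is 1.555/2 = 0.777 and the half-width ratio is 0.777 × 0.973 = 0.76, which matches the simulated 0.76. For 60/90/100, √[(3600 + 8100 + 10000)/3] = √7233 = 85.05, so the Day 28 SE ratio is 0.851.

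| SDs | Day 28 SE ratio | Approximate coverage | Simulated Day 28 coverage |
|---|---|---|---|
| 1:1:1 | 1.000 | 95.3% | 94–95% |
| 90/95/100 | 0.951 | 94.1% | 93–94% |
| 60/90/100 | 0.851 | 90.9% | 89–91% |
| 1:1.5:2 | 0.777 | 87.7% | 86–87% (20,000 trials) |

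A 200-trial run of the last case gave 82.5%. Its Monte Carlo standard error is √(0.825 × 0.175/200) = 2.7 points, so the larger run is the better guide. Day 1 intervals err the other way in the last two rows, with coverage of about 99% or more.

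**The case against.** The case for leaving this alone is substantial. The code is offered as a sample open to change, and the model in the text is sound. Protocol 3.10 requires statistical quality control checks. The SAP states that no formal inferential test will be performed, and the sample size is not statistically determined. Subjects stay in-house from Day -3 to Day 35, so a missing Day 14 with Day 28 present should be uncommon. Not imputing missing data does not mean that rows are deleted. The one order that the SAP does state, for listings, is treatment, subject, time point, and that order would be harmless with complete data.

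Most of this stands and limits the size of the point. It does not remove it. Sample code is there to be copied, and SAP 5 allows subjects to be partially excluded from the analysis, which could remove a single earlier day.

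Four stronger readings are tempting, and the documents do not support them:

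- **That the code contradicts a stated repeated factor.** The text lists day as a fixed effect and makes subject the repeated-measures unit. That day should index the covariance is an inference from the by-day contrasts.
- **That the failure is silent.** This holds only for a numeric subject variable. Protocol 3.8.1 uses randomization numbers with leading zeros, such as 0101, so character storage is plausible, and the step should then stop.
- **That these are the only between-group PD estimates.** Section numbers in the public SAP skip from 4.3 to 4.5 and from 6.8 to 6.10, so this cannot be established.
- **That UGE0-24 uses this very code.** The SAP says only that its MMRM is similar, and names AUEC0-24.

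**Conclusion.** The omissions are real and the code should not be run as printed, but the harm is conditional and usually small. The realistic route, a few earlier records absent from a properly sorted dataset, shifts the Day 28 standard error or half-width by about 1–4% on average. Material under-coverage needs two things together: a dataset not sorted by subject, and variances that clearly differ by day. A reader might infer that the planned intervals will be wrong. The documents support only that they could be.

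These sizes rest on assumed SDs, correlations and numbers of absent records, and on the software behaviour described above. This is a minor correction to sample code in a Phase 1 study without formal testing.

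**What to change.** In the MMRM code of SAP 6.8:

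- `CLASS SUBJECT DAY TREATMENT;`
- `REPEATED DAY / SUBJECT=SUBJECT(TREATMENT) TYPE=UN;`

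Use one subject variable name, SUBJID or SUBJECT, in both code blocks of the section. In SAP 6.10.6, state that the UGE0-24 MMRM uses the same corrected code, and reconcile the AUEC0-24 reference with the AUEC0-4 model shown.

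The cost is a few words in the SAP, with no change to the protocol, the data collected or the model described in the text. Results from complete data sorted by subject then day are unchanged (half-width ratio 1.000). Otherwise the dependence on row order is removed.

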# 3.4 Discontinuation of Subjects from the Study/Study Drug

A subject may prematurely discontinue from the study/study drug administration under the following conditions:

- Withdrawal by Subject: subjects have the right to withdraw from the study at any time. However, if a subject withdrew because of an AE, the reason for discontinuation should be documented as an AE.
- Investigator Decision: the Investigator decides a subject should be discontinued. The reason for the decision should be documented.
- Adverse Event: a medical condition(s), requiring study drug discontinuation, whether or not related to the study drug (e.g., COVID-19).
- Non-compliance with Study Drug

- Protocol Deviation: the subject is non-compliant with protocol requirements, as determined by Akros or the Investigator. These are limited to important protocol deviations (e.g., Good Clinical Practice [GCP] deviations, important deviations related to the inclusion or exclusion criteria).
- Lost to Follow-up
- Death
- Study Terminated by Sponsor: the sponsor may suspend or terminate the study or part of the study at any time for any reason (see Section 3.5).
- Pregnancy
- Other: (e.g., subjects who have taken placebo on Day -1 but are not randomized on Day 1 into Cohort 3 will be discontinued from the study).

Subjects who test positive for COVID-19 after study drug administration on Day 1 will be discontinued from study drug and appropriate follow-up actions will be taken as per the site's standard operating procedures and COVID-19 management guidelines.

Subjects who discontinue the study/study drug after placebo adminstration on Day -1 but before randomization on Day 1 will be discharged from the site at the discretion of the Investigator. These subjects will be requested to complete a follow-up telephone call from the site within 7 days after being discontinued from the study. The follow-up call will be conducted to assess the general health of the subject. In addition, the subject will be asked to report if any AEs occurred, if any medication was taken and if there were any changes to medications during the 7 day period after the subject was discontinued from the study.

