5 ANALYSIS POPULATIONS

Randomized Population: All subjects randomized to receive JTT-662 or placebo on Day 1.

Safety Population: All subjects who receive at least one dose of JTT-662 or placebo, including those who do not complete the study. Subjects who were dosed on Day -1 only (placebo run-in) will also be included in the safety population.

Pharmacokinetic Population: All randomized subjects who received at least one dose of JTT-662 starting on Day 1, and have evaluable JTT-662 plasma concentration data. Subjects will be excluded or partially excluded from the statistical analysis of PK parameters if they significantly violated the inclusion or exclusion criteria or deviated significantly from the protocol.

Pharmacodynamic Population: All randomized subjects who received at least one dose of JTT-662 or placebo starting on Day 1, and have evaluable PD data to facilitate the calculation of PD parameters. Subjects will be excluded or partially excluded from the statistical analysis if they significantly violated the inclusion or exclusion criteria or deviated significantly from the protocol.

STATISTICAL METHODS

The statistical analysis will be conducted following the principles specified in the International Council for Harmonisation of Technical Requirements for Pharmaceuticals for Human Use (ICH) Topic E9 Statistical Principles for Clinical Trials (CPMP/ICH/363/96).

No formal inferential test will be performed in this Phase 1 study.

All statistical tabulations and analyses will be performed using Any changes to the analyses described in this plan will be detailed in the CSR.

All results collected in the database will be presented in listings. All continuous data will be listed with the same precision as will be presented in the database. Data listings will be sorted by treatment group, subject ID, and time point.

Unless otherwise noted, continuous variables will be summarized using number of non-missing observations (n), arithmetic mean (mean), standard deviation (SD), median, minimum, and maximum. For PK parameters, summary statistics will also include the coefficient of variation (CV%) and geometric mean (geometric mean will not be presented for t_{max}). For plasma concentrations and PD parameters, summary statistics will also include the CV%. Categorical variables will be summarized using the frequency count and the percentage of subjects in each category.

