All subjects randomized to placebo on Day 1 will be included in the placebo treatment group unless otherwise specified.

In the data listings, study day relative to first dose of study drug on Day 1 may be presented. Study day relative to first dose of study drug on Day 1 will be calculated as: event date – first dose date on Day 1 (+ 1 if event date \geq first dose date on Day 1).

Baseline will be the latest non-missing measurement prior to the first dose of study drug on Day 1, unless otherwise specified

For safety summaries, the unscheduled and repeat assessments will not be summarized; however, all results will be included in the data listings.

Disposition, demographics, and baseline characteristics and all categorical safety parameters will be summarized by each treatment group and overall.

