Treatment-emergent PCS values will be summarized, presenting the number and percentage of subjects who had at least one PCS value after study drug administration on Day 1. The denominator is always the number of subjects in the safety population, regardless of whether the subject had any post-baseline measurements. The numerator is any PCS value in the treatment-emergent period if the baseline is normal or missing; and is any worsening PCS value in the treatment-emergent period if the baseline is also a PCS value.

A worsening PCS is defined as a > (<) 0 change from baseline if a high (low) value indicating undesirable outcome; or the PCS value is in the opposite direction of the baseline PCS value.

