6.10.2 Safety Laboratory Assessments

Observed and change from baseline for each parameter of continuous safety laboratory values (hematology, serum chemistry, coagulation, and urinalysis) will be summarized by treatment group at each time point using descriptive statistics.

Any post-baseline abnormal laboratory finding will be assessed to calculate overall treatment-emergent potentially clinically significant (TEPCS) status as described in tables PCS Criteria for Laboratory Parameters. Values assessed as TEPCS will be summarized categorically per treatment group and overall.

A listing of all safety laboratory data for each subject at each time point will be presented. Out of range values and PCS values will be flagged in the data listing. Safety laboratory values that are outside the normal ranges will be presented in a separate listing together with normal ranges values. For the listing presenting all abnormal values, if a subject has any abnormal value for a test, all values of that test of the subject will be presented.

Statistical Analysis Plan - Protocol No. AT662-U-20-003

Qualitative urine parameters are generally reported by a descriptive score, which may differ between laboratories. For pooling the data, a four-point scale is used. A clinical review will be performed on the mapping of the descriptive scores to the four-point scale; and the descriptive scores will be remapped where appropriate. The four-point scale will be used in the summary of the PCS abnormality analysis.

Five-point scale	Four-point scale
Negative	Negative
Trace	Rare/Mild
1+	Rare/Mild
2+	Moderate
3+	Severe

The mean profile by treatment group will be presented for selected laboratory parameters.

If the non-numeric result is reported for quantitative laboratory parameter then for summary and analysis it will be changed as follows into numerical value:

- a) If less than '<' sign is used then the value will be reduced by 1 point from the last precision digit
- b) If greater than '>' sign is used then 1 point will be added to the last precision digit.

Eg: if the laboratory parameter is reported to 2 decimal precision, <40.01 then for summary and analysis it will be treated as 40.00, if laboratory parameter is reported as whole number >40 then it will be considered as 41 and if the parameter is reported with 1 decimal precision <40.1 then it will be considered as 40.0.

Potentially Clinically Significant Criteria for Laboratory Parameters

Hematology

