6.10.3 Vital Signs and Body Weight

Observed values and change from baseline for continuous vital signs parameters (blood pressure, heart rate, respiratory rate, and temperature) and weight will be summarized by treatment group at each time point using descriptive statistics. Percent change from baseline in weight will also be summarized descriptively by treatment group.

Any post-baseline abnormal vital sign finding assessed as TEPCS values will also be summarized. Vital sign data will be listed by subject and time point collected. In addition, values meeting PCS criteria will be flagged in the listing.

Potentially Clinically Significant Criteria for Vital Sign Values

Parameter		
CDISC Code	SDTM	Definition
C49676	Pulse Rate	Pulse rate
C25298	Systolic Blood Pressure	Systolic blood pressure
C25299	Diastolic Blood Pressure	Diastolic blood pressure
C49678	Respiratory Rate	Respiratory rate
C25206	Temperature	Body temperature
C25208	Weight	Body weight

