6.10.4 Electrocardiogram

Observed values and change from baseline for each parameter of continuous ECG parameters (RR interval, PR interval, QRS duration, QT interval, and QTcF interval) will be summarized by treatment group at each time point using descriptive statistics.

The overall ECG interpretation will be summarized by treatment group at each time point using descriptive statistics.

Any post-baseline abnormal ECG findings assessed as TEPCS values will also be summarized.

ECG data will be listed by subject at each visit and time point collected with indicated clinically significant results. In addition, values meeting PCS criteria will be flagged in listing.

Potentially Clinically Significant Criteria for ECG Parameters

Parameter		
CDISC Code	SDTM	Definition
C117773	PR Interval, Aggregate	PR
C117791	RR Interval, Aggregate	RR
C117779	QRS Duration, Aggregate	QRS
C117783	QT Interval, Aggregate	QT interval
C117784	QTcB Interval, Aggregate	Bazett-corrected QT interval
C117786	QTcF Interval, Aggregate	Fridericia-corrected QT interval

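### If k subjects are dosed on Day -1 only, the overall treatment-emergent PCS percentage is understated by k/(N+k) in relative terms, because they are in the denominator but cannot be events

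*SAP*

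**What the plan says.** **Numerator.** SAP 6.10 defines the TEPCS summary as "presenting the number and percentage of subjects who had at least one PCS value after study drug administration on Day 1".

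**Denominator.** The same paragraph adds: "The denominator is always the number of subjects in the safety population, regardless of whether the subject had any post-baseline measurements".

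**Population.** SAP 5 says: "Subjects who were dosed on Day -1 only (placebo run-in) will also be included in the safety population". The protocol's definition in 3.9.1 has no such sentence; the SAP makes the inclusion explicit.

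**Columns.** The general part of the SAP's Statistical Methods section requires: "Disposition, demographics, and baseline characteristics and all categorical safety parameters will be summarized by each treatment group and overall". SAP 6.10.2 repeats this for laboratory data: "Values assessed as TEPCS will be summarized categorically per treatment group and overall". For vital signs, SAP 6.10.3 says "Any post-baseline abnormal vital sign finding assessed as TEPCS values will also be summarized", and for ECG, SAP 6.10.4 says "Any post-baseline abnormal ECG findings assessed as TEPCS values will also be summarized". Neither names the columns, so the general rule governs both.

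**Who the extra subjects are.** Protocol 3.4 foresees them. Its example of another reason for discontinuation is that "subjects who have taken placebo on Day -1 but are not randomized on Day 1 into Cohort 3 will be discontinued from the study". Anyone who leaves between the Day -1 placebo and randomization is discharged at the investigator's discretion and asked only for a telephone follow-up.

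**The concern.** The numerator starts at the Day 1 dose, while the denominator starts at the Day -1 placebo. A subject who took only the run-in placebo has no period in which a TEPCS value could arise. The telephone call yields no laboratory, vital sign or ECG value, and the SAP keeps unscheduled assessments out of safety summaries. Such a subject is a non-event by construction.

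The adverse event tables avoid the problem. SAP 6.10.1 gives the run-in its own group and starts each treatment group at Day 1 dosing. The TEPCS tables have no run-in group.

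The overall TEPCS percentage would therefore depend partly on how many subjects took the Day -1 placebo and were never dosed afterwards, which says nothing about safety on treatment. The error can only go downward, on a safety measure.

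**Working it through.** **Inputs**
- Planned number randomized: 3 cohorts × (9 active + 3 placebo) = 36, as stated in SAP 6.1 and Protocol 3.9.2. The documents give no TEPCS rate to reproduce.
- N: subjects dosed from Day 1. I take N = 36, and N = 40 as an assumed case with 4 replacements.
- k: subjects dosed on Day -1 only. Not stated, so assumed. Same-day entry into Cohort 2 for subjects not randomized into Cohort 1 (Protocol 3.8.1) lowers k. Re-screening (Protocol 3.6.2) may lower it too, but the documents do not say how the first Day -1 exposure would then be counted.
- x: subjects with a TEPCS value; illustrative.

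**Formulas**
- Rate among subjects who can have an event: x/N.
- Rate under the SAP rule, with overall read as the whole safety population: x/(N+k).
- Relative shortfall: 1 − [x/(N+k)]/[x/N] = k/(N+k), whatever x is.
- Absolute shortfall: (x/N) × k/(N+k).

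**Results, N = 36**

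| k (assumed) | Relative shortfall | True 4/36 = 11.1% reads | True 8/36 = 22.2% reads |
|---|---|---|---|
| 0 | 0% | 11.1% | 22.2% |
| 1 | 1/37 = 2.7% | 4/37 = 10.8% | 8/37 = 21.6% |
| 2 | 2/38 = 5.3% | 4/38 = 10.5% | 8/38 = 21.1% |
| 3 | 3/39 = 7.7% | 4/39 = 10.3% | 8/39 = 20.5% |

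At k = 3 the absolute loss is 11.1% × 3/39 = 0.9 points in the first example and 22.2% × 3/39 = 1.7 points in the second.

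**N = 40.** The relative shortfall is 1/41 = 2.4%, 2/42 = 4.8% and 3/43 = 7.0% for k = 1, 2 and 3.

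**Wider range.** Nothing in the documents caps k at 3. With N = 36 the relative shortfall is 6/42 = 14.3% at k = 6 and 9/45 = 20.0% at k = 9.

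**Arms.** The SAP defines the placebo group by randomization on Day 1, so a subject never randomized is in no arm: 2/9 = 22.2% stays 2/9. A subject randomized but not dosed on Day 1 is still in the safety population through the Day -1 dose. If tabulated in the assigned arm beside nine dosed subjects, that subject turns 2/9 = 22.2% into 2/10 = 20.0%. The schedule places randomization and the first dose both at Hour 0 of Day 1, so this should be rare.

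**The case against.** The strongest reply is that the SAP never defines the overall column. Taken literally, the denominator rule would divide every arm by the whole safety population. Nobody would do that, so the rule must mean the safety-population subjects belonging to the column. On that reading, overall could be the sum of the treatment groups, and Day -1-only subjects belong to none of them. This reading is possible. It fits less well with the word *always*, and with SAP 6.2 and 6.4, which present disposition and demographics by treatment group and overall for the safety population. If the narrower reading was intended, the text still lets two programmers report different totals, and the same sentence settles it.

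The convention is also open and largely reversible. The tables give counts as well as percentages, and SAP 6.2 tabulates the population sizes. Unless someone was randomized and not dosed, a reader can recompute x/N. That stands, and limits the harm.

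Finally, nothing rests on the column. It pools placebo with three dose levels, the SAP disclaims formal inferential testing, and no section ties the dose review to a pooled TEPCS percentage. That also stands and keeps the point minor.

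A reader might go further and infer that the TEPCS comparison of active doses with placebo is diluted. The documents do not support that for subjects never randomized, because they enter no arm.

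**Conclusion.** The mismatch is in the SAP as written: Day 1 events over a Day -1 population. With N = 36 the overall TEPCS percentage is low by 2.7%, 5.3% or 7.7% in relative terms for k = 1, 2 or 3. These are not percentage points: at a true 22.2% the loss is 0.6, 1.2 or 1.7 points. The result rests on two assumptions: that k is above zero, which the protocol foresees but does not quantify, and that overall means the whole safety population.

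Two stronger statements are tempting and unsupported. One is that the overall rate will be understated; if k = 0 there is no effect. The other is that arm rates are safe in every case; that holds for subjects never randomized, but a subject randomized and not dosed on Day 1 could dilute an arm. Severity is minor: the column is descriptive, and never-randomized subjects alter no dose-placebo comparison.

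**What to change.** Add one sentence to SAP 6.10: for all TEPCS summaries (laboratory, vital signs and ECG; each arm and overall), the denominator is the number of safety-population subjects who received study drug on or after Day 1, whether or not they have post-baseline measurements.

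This keeps the existing choice to count dosed subjects who lack later values, removes subjects who cannot be events, settles what overall means in these tables, and covers the randomized-but-undosed case within arms.

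The cost is one sentence and one population flag, with no new data. The drawback is that the overall TEPCS total may differ from the safety-population total shown elsewhere, so the tables need a footnote giving the reason.
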